Demographic and clinical data will be recorded into a table. The patient will be instructed not to wash or wipe the topical agent off. The time and date of the start of treatment applied and subsequent treatments at 12 hour intervals will be documented. At the start of the study and at each 12 hour interval, the investigator will observe for signs of phlebitis using the Visual Infusion Phlebitis scoring tool [Appendix 2], before application of the next treatment. The study investigators will be the only ones applying the treatment/control and completing the data collection form [Appendix 3] every 12 hours. Patient identifiers (name and NRIC) will be verified before every application of the treatment/control and the completion of the data collection form.

Application of the treatment or control will be made every 12 hours for up to 72 hours, where the IV cannula will then be removed according to hospital guidelines. The IV cannula site will be observed, every 12 hours for up to 24 hours post IV cannula removal, for phlebitis or complications.

Patients will be withdrawn from the study the moment they show signs of adverse reactions from the topical treatment or control.

Participants will be involved in the study for a maximum of 96 hours. If the IV cannula is removed accidentally or not due to phlebitis before the 72-hour period is up, re-insertion of a new cannula and re-application of oils will not be done on a new site. The patient's IV cannula site will continue to be observed for 24 hours at 12-hour intervals after cannula removal. The partial data will be kept and analysed. If the patient is discharged before the 96 hour observation period is up, the 24 hour post-removal observation will continue to be carried out at 12 hour intervals, via phone call or video call. The patients' phone numbers will be obtained during the informed consent process, only for follow up purposes.

The application of either sesame oil or liquid paraffin oil is not part of the routine procedures or standard of care in the ward, and will only be applied for the purpose of this research. Both the sesame oil and liquid paraffin oil are marketed products and will be used as per label.

The study is estimated to continue for two years, commencing in February 2022 and ending in December 2023.

At no point of the study will any audio or video recording take place.

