### 8. SAMPLE SIZE AND STATISTICAL METHODS

#### 8.1. Determination of Sample Size

Using a power analysis of 20% and a difference of 35%, a sample size of 44 participants is required if subgroup analysis is not required. We then rounded it up to 100 to account for an attrition rate of 5%.

Data will be analysed with the Statistical Package for Social Science (SPSS) software program (v. 28) using descriptive statistics such as relative and absolute frequencies, mean and standard deviation, and inferential statistics such as Chi-square, independent t-test and Hazard ratio.

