#### 8.2. Statistical and Analytical Plans

#### a. General Considerations

The distribution and dispersion of the data will be examined through descriptive numerical summaries and graphical tools such as scatter plots, via SPSS. The data will then be analysed using descriptive statistics such as relative and absolute frequencies, mean and standard deviation, and inferential statistics such as Chi-square, independent t-test and Hazard ratio.

As missing data can potentially spoil or invalidate a study, we will spare no effort in minimising incomplete or missing data. All data will be carefully inspected to identify missing items and outliers. In the analysis of incomplete data, we will consult with a biostatistician regarding the use of incomplete-data analysis strategies that will allow us to utilise the available information effectively.

b. Safety Analyses

All adverse events, such as the development of allergic reactions to the oils, leading to the participant's withdrawal from the study will be collected and tabulated. Incidences and severity of phlebitis experienced during the course of the study will also be collected and tabulated. All adverse reactions and phlebitis incidences will be tabulated for both the treatment and control group. The extent and severity of symptoms will also be documented. For phlebitis incidences, the severity will be assessed with the Visual Infusion Phlebitis (VIP) scoring tool [Appendix 2]. The number of adverse reactions will be summarised for both the treatment and control group. Frequency counts and percentages will be calculated and reported.

c. Interim Analyses

We will compare treatment groups on descriptive and clinical characteristics at baseline to ensure that randomisation has succeeded. SPSS will be used for group comparisons, descriptive calculations and conditional regression modelling. We will examine the distributions of all important variables at baseline and at the end of the data collection period, to assess for covariate imbalance. Formal statistical methods to test for selection bias will be used.

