#### Visual Infusion Phlebitis Scoring Tool

# **Visual Infusion Phlebitis Scoring Tool**

IV site appears healthy	0	No signs of phlebitis OBSERVE CANNULA
One of the following signs is evident: • Slight pain near IV site OR • Slight redness near IV site	1	Possible first signs of phlebitis RESITE CANNULA
Two       of the following are evident:         •       Pain at IV site         •       Redness         •       Swelling	2	Early stage of phlebitis RESITE CANNULA
All of the following signs are evident: • Pain at IV site • Redness • Swelling	3	Medium stage of phlebitis INITIATE TREATMENT RESITE CANNULA

 
All of the following signs are evident and extensive:
 
Pain at IV site
 
Redness
 
Swelling
 
Palpable venous cord
 
	4	Advanced stage of phlebitis or start of thrombophlebitis INITIATE TREATMENT RESITE CANNULA
All of the following signs are evident and extensive: 
 
Pain at IV site
 
Redness
 
Swelling
 
Palpable venous cord
 
Pyrexia
 
	5	Advanced stage of thrombophlebitis INITIATE TREATMENT RESITE CANNULA

Tool Developed by Andrew Jackson – Consultant Nurse Intravenous Therapy & Care, The Botherham NHS Foundation

This tool was modified for use in this study.

Right arm	Left arm	Participant No:	
		Age:	
		Gender: Male / Female Race:	
		Medications	
		Oral / IV anticoagulants (if any):	
		IV Insertion	
		 Date: Time:	
		Size:	
		Site: Inserted at :(Dept)	
		IV Removal	
Mark IV Conn	Date: Time:		
Mark IV Cann	Reason:		

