# **Data Collection Form**

IV plug assessment	Insertion Date		Day 1 Date		Day 2 Date		Day 3 (Removal) Date		Post Removal
									Date
	0 hrs	12 hrs	24 hrs	36 hrs	48 hrs	60hrs	72hrs (Removal)	12 hrs post removal	24 hrs post removal
VIP Score (0-5)									
Treatment/ Control applied (Please tick)									
Current drug infusion									
Other drugs administered via this IV Cannula in the past 12hrs									
Initials

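### Section 8.2b reports oil reactions only as counts and percentages per arm, although the number of oil applications probably depends on whether phlebitis occurs

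*Combined protocol and SAP*

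**What the plan says.** The safety summary in Section 8.2b is descriptive: "The number of adverse reactions will be summarised for both the treatment and control group. Frequency counts and percentages will be calculated and reported". No number of applications or time at risk is mentioned. The hazard ratio appears in Sections 8.1 and 8.2a as a general method and is not assigned to reactions.

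On exposure, Section 5 states: "Application of the treatment or control will be made every 12 hours for up to 72 hours", with removal of the cannula at that point. On observation it adds: "The IV cannula site will be observed, every 12 hours for up to 24 hours post IV cannula removal, for phlebitis or complications". Total participation is capped at 96 hours.

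The link between phlebitis and removal has to be pieced together:

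- Section 1 says that phlebitis often leads to early withdrawal and reinsertion of the cannula.
- The Appendix 2 tool already reads, at score 1: "Possible first signs of phlebitis RESITE CANNULA". Every higher score carries the same instruction to re-site.
- Section 4.4 excludes a patient's later cannulas from the study.
- The early-removal rule in Section 5 covers only removals that are accidental or not due to phlebitis. It is silent on what happens to the oil once phlebitis is seen.

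**The concern.** If phlebitis ends oil application, the length of exposure is itself a consequence of the efficacy outcome. The arm with less phlebitis keeps its cannulas longer, receives more applications and is observed for longer in total. Its percentage of patients with a reaction can then be higher even when the two oils are equally irritant. In the other direction, if sesame oil led to more phlebitis, its shorter exposure could mask a real excess of reactions.

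Section 3 lists skin irritation as the only potential risk, and the table in Section 8.2b is the only planned summary of it. Readers will set the two percentages side by side whether or not a test is planned.

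**Working it through.** The plan states no reaction rate, exposure or safety precision, so there is no figure of its own to reproduce. The check asks how far crude percentages diverge when the two oils carry the same risk per application.

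**Inputs from the documents.** Applications every 12 hours for up to 72 hours, and 24 hours of observation after removal (Section 5). Phlebitis of 78% v 39% in a cited study of patients on IV amiodarone (Section 1). A sizing difference of 35% (Section 8.1), read here as percentage points because the arm rates are not given. A general phlebitis range of 5 to 75% (Section 1).

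**Assumptions.** Six applications, at 0 to 60 hours. Constant phlebitis hazard per interval. Oil stops at the check where phlebitis is seen. No other cause of early removal. The same reaction risk q at each application in both arms. A patient leaves at the first reaction, as Section 5 provides.

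**Formulas.** With 72-hour phlebitis incidence p:

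- hazard per interval: h = 1 − (1 − p)^(1/6)
- mean applications, ignoring the few lost to reactions: A = Σ (1 − h)^k for k = 0 to 5, which equals p/h
- mean hours observed: 12A + 24
- crude reaction proportion: R = q × Σ [(1 − q)(1 − h)]^k for k = 0 to 5

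**Worked case, 78% v 39%.**

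- Control: h = 1 − 0.22^(1/6) = 0.223, so A = 3.50 and hours = 12 × 3.50 + 24 = 66.0.
- Sesame: h = 1 − 0.61^(1/6) = 0.079, so A = 4.93 and hours = 83.2.
- Ratio of applications: 4.93/3.50 = 1.41.
- At q = 1%: R = 3.44% v 4.82%, ratio 1.40. At q = 5%: 16.0% v 22.0%, ratio 1.38.

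**Other rates.**

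| Phlebitis, control v sesame | Mean applications | Ratio |
|---|---|---|
| 78% v 39% | 3.50 v 4.93 | 1.41 |
| 75% v 40% | 3.64 v 4.90 | 1.35 |
| 50% v 15% | 4.58 v 5.61 | 1.22 |
| 35% v 0% | 5.05 v 6.00 | 1.19 |
| 20% v 10% | 5.48 v 5.74 | 1.05 |
| 10% v 5% | 5.74 v 5.87 | 1.02 |

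For small q the crude reaction ratio follows the application ratio closely.

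**Effect of relaxing the assumptions.**

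- *Timing of reactions (78% v 39%).* With 2% risk at the first application and none later, the ratio is 1.00. With 2% at the first and 0.5% at each later one, it is 1.22.
- *Other early removals.* The plan gives no rate. Assuming a 50% chance over 72 hours in both arms, 78% v 39% falls from 1.41 to 1.34, and 50% v 15% from 1.22 to 1.19.

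**What a rate per application does.** Dividing R by the mean applications actually given, Σ [(1 − q)(1 − h)]^k, returns q in both arms. At q = 1% that is one reaction per 100 applications in each arm, so under these assumptions the exposure effect disappears.

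**The case against.** Several points on the other side stand and limit the claim.

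- A reader might infer that the plan makes a biased between-arm safety comparison. It does not: Section 8.2b tabulates reactions by arm, with no test, margin or safety conclusion attached. The percentage of patients with a reaction validly describes what happens under the strategy as used, including longer use because the cannula lasts longer.
- A reader might infer that monitoring stops when phlebitis is found. Section 5 keeps the site under observation for up to 24 hours after removal, and Section 6.3 follows reactions until they resolve. Only the total observation time differs.
- That oil stops at phlebitis is inferred from Sections 1 and 4.4 and Appendix 2. Section 5 does not state it.
- The largest ratio comes from a study of one infused drug, with a control rate of 78%, above the 5 to 75% range in Section 1. This trial recruits cardiology inpatients more generally. At low phlebitis rates the effect is 2 to 5%.
- Events will be few. At 78% v 39% and q = 1%, expected reactions are 50 × 0.0344 = 1.7 v 50 × 0.0482 = 2.4 if the 100 patients of Section 8.1 are enrolled, and 11.2 v 15.7 with 325 per arm (the 650 of Section 4.1). Were anyone to test the gap, the chance of significance would be about 5% and 14%.

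These points rule out a flat statement that an effective sesame oil will look less safe. They leave standing that a percentage without the exposure behind it cannot be read as a measure of irritancy, and that the plan does not ask for the exposure.

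**Conclusion.** The point holds in a conditional form and is a cheap improvement. If phlebitis ends application at the study site, the crude ratio for equally irritant oils is about 1.4 at 78% v 39% phlebitis, about 1.2 to 1.35 for 35-point differences and about 1.05 at 20% v 10%. These sizes rest on a constant risk per application and on phlebitis being the only cause of early removal. Other removals shrink them, and they vanish if reactions arise only at first contact.

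A reader might also conclude that the percentages should give way to the rate as the basis of the safety statement. The documents do not support that: the rate depends on an assumption the plan gives no evidence for, and it will be imprecise. The efficacy analysis is not affected.

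**What to change.** In Section 8.2b, keep the counts and percentages. Add for each arm the total number of oil applications, the total hours observed, and adverse reactions per 100 applications with an exact (Poisson) 95% confidence interval. State that any difference between arms will be interpreted from both measures together.

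Separately, reconcile Sections 1, 4.4 and 5 with Appendix 2, so that the document states what happens to oil application and observation once phlebitis is seen.

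The data are already planned. The data collection form has a row marked "Treatment/ Control applied (Please tick" at each visit and records the date and time of IV removal. Section 5 has the date and time of the first and later applications documented. The cost is a sentence or two in 8.2b and a few table rows, with no extra visits or patients.

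The downside is that the rate assumes a roughly constant risk per application and will be imprecise with few events. For example, 2 reactions in 50 × 3.44 = 172 applications have exact Poisson limits of 0.242 and 7.225 events, that is 0.14 to 4.2 per 100 applications. This is why the percentages should stay beside it.

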### 9. DIRECT ACCESS TO SOURCE DATA/DOCUMENTS

The investigators and the National Heart Centre of Singapore will permit study-related monitoring, audits and/or IRB review and regulatory inspection(s), providing direct access to source data/document. All physical data required will be accessed through the primary investigator.

### 10. QUALITY CONTROL AND QUALITY ASSURANCE

The primary investigator will review all physical data and conduct random audits to assess for adherence with the protocol. She will also assess all data weekly for accuracy and completeness.

### 11. ETHICAL CONSIDERATIONS

This study will be conducted in accordance with the ethical principles that have their origin in the Declaration of Helsinki and that are consistent with the Good Clinical Practice and the applicable regulatory requirements.

This final Study Protocol, including the final version of the Participant Information and Consent Form, must be approved in writing by the Centralised Institutional Review Board (CIRB), prior to enrolment of any patient into the study.

The principal investigator is responsible for informing the CIRB of any amendments to the protocol or other study-related documents, as per local requirement.

#### **11.1. Informed Consent**

Informed consent will be taken at the patient's bedside by an investigator of the study, in the presence of a witness, with drawn curtains to maintain privacy, reduce distractions and prevent undue influence from other individuals within the ward. The participant will be given time to consider their participation before giving their response to the investigator at the bedside. If they require more time for consideration, the investigator will leave the bedside and contact them again within 12 hours of IV cannula insertion to confirm recruitment. The investigator will emphasise the patient's right to make their own decision with regards to participating in the study. All details of the study and risks and benefits will be provided without any pressure on the patient to be recruited.

#### 11.2. Confidentiality of Data and Patient Records

All hardcopy data collected will be stored in a locked cabinet within the National Heart Centre of Singapore. Only the principal investigator will have access to the locked cabinet. Investigators may access the data via the principal investigator. Electronic data will be stored on a password protected laptop belonging to the principal investigator, and access to the data will be restricted to the investigators of this research study.

#### 12. PUBLICATIONS

All investigators involved in this study will be given authorship for scientific publications. Other persons who may have contributed in some capacity, such as those who may have provided advice with regards to the research, or assisted with data analysis, will be acknowledged with their approval. The contributions of each author will be reviewed thoroughly to ensure that they meet the criteria of authorship for the respective journals. Should a journal require assurances that all non-author contributions agree to being named in the acknowledgements, or that no non-author contributors have been omitted from the acknowledgements, signed agreements will be provided on request.

### **13. RETENTION OF STUDY DOCUMENTS**

Records for all participants, including CRFs, all source documentation (containing evidence to study eligibility, history and physical findings, etc.) as well as IRB records and other regulatory documentation will be retained by the PI in a secure storage facility. The records will be accessible for inspection and copying by authorized authorities. The physical research data will be kept under lock and key for 7 years after the completion of the research study or date of publication of the research using the research data, whichever is later. After which, all data will be destroyed. Hardcopies will be shredded and soft copies will be deleted.

#### 14. FUNDING and INSURANCE

#### Grant

i. Name of Grant Agency:	National Heart Centre of Singapore Pte Ltd (NHCS)
ii. Grant Name:	Lim Suh Fen Cardiovascular Research and Education Fund
iii. Amount:	\$20090
iv.Grant Reference Number	07/FY2021/EX/91-A145(a) and 07/FY2021/EX(SLP)/91A145(b)

#### Visual Infusion Phlebitis Scoring Tool

# **Visual Infusion Phlebitis Scoring Tool**

IV site appears healthy	0	No signs of phlebitis OBSERVE CANNULA
One of the following signs is evident: • Slight pain near IV site OR • Slight redness near IV site	1	Possible first signs of phlebitis RESITE CANNULA
Two       of the following are evident:         •       Pain at IV site         •       Redness         •       Swelling	2	Early stage of phlebitis RESITE CANNULA
All of the following signs are evident: • Pain at IV site • Redness • Swelling	3	Medium stage of phlebitis INITIATE TREATMENT RESITE CANNULA

 
All of the following signs are evident and extensive:
 
Pain at IV site
 
Redness
 
Swelling
 
Palpable venous cord
 
	4	Advanced stage of phlebitis or start of thrombophlebitis INITIATE TREATMENT RESITE CANNULA
All of the following signs are evident and extensive: 
 
Pain at IV site
 
Redness
 
Swelling
 
Palpable venous cord
 
Pyrexia
 
	5	Advanced stage of thrombophlebitis INITIATE TREATMENT RESITE CANNULA

Tool Developed by Andrew Jackson – Consultant Nurse Intravenous Therapy & Care, The Botherham NHS Foundation

This tool was modified for use in this study.

Right arm	Left arm	Participant No:	
		Age:	
		Gender: Male / Female Race:	
		Medications	
		Oral / IV anticoagulants (if any):	
		IV Insertion	
		 Date: Time:	
		Size:	
		Site: Inserted at :(Dept)	
		IV Removal	
Mark IV Conn	Date: Time:		
Mark IV Cann	Reason:		

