#### 4.3. Inclusion Criteria

- Age 21-80
- Patients must speak and understand either English or Mandarin
- Patients who possess a peripheral IV cannula
- IV cannula must have been inserted for less than 12 hours
- IV cannula must be on an upper extremity
- IV cannula must be patent
- IV cannula sites must show no signs of redness, swelling, pain, a palpable venous cord or pyrexia
- Patient must be admitted to a cardiology ward in the National Heart Centre Singapore

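### The modified VIP tool has no score for isolated swelling, an isolated palpable cord, or the two together, and the form keeps only the total, so these sites are scored at the assessor's discretion and cannot be rescored

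*Combined protocol and SAP*

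**What the plan says.** Phlebitis incidence and severity, assessed every 12 hours, are the study's objectives (Section 2). Section 5 makes the VIP tool the instrument, and no other phlebitis measure is described. Appendix 2 gives these rows:

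- Score 0: "IV site appears healthy".
- Score 1: "One of the following signs is evident", followed by two options, "Slight pain near IV site OR" "Slight redness near IV site".
- Score 2, labelled "Early stage of phlebitis": two of pain, redness and swelling.
- Score 3: all three of these.
- Score 4: all three, extensive, plus a palpable cord.
- Score 5: the same four signs plus pyrexia.

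Below the table stands the note "This tool was modified for use in this study", so the rows are the study's own to define.

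The entry criterion in Section 4.3 reads "IV cannula sites must show no signs of redness, swelling, pain, a palpable venous cord or pyrexia", and Section 4.2 ends recruitment if any one of these is found. Section 1 counts oedema and palpable cords among the signs of phlebitis and says that one sign, in varying degree, may be enough.

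On who assesses, Section 5 says: "The study investigators will be the only ones applying the treatment/control and completing the data collection form". The data collection form has one outcome field per time point, the VIP score from 0 to 5. Section 8.2(b) undertakes to document how extensive and severe symptoms are.

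**The concern.** A score can be analysed only if every site maps to one value by rule. Here, two findings that the protocol regards as signs of phlebitis have no value when they occur without pain or redness. The same swollen site would be refused at screening and would have no defined score 12 hours later.

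The gap is filled by judgement, within the team that applies the oil and at the same visit. Different investigators may fill it differently, and nothing in the text says how. Because the form keeps the total and not the signs, a disputed score could not be re-derived, and a sensitivity analysis under another scoring rule would not be possible. This affects the only outcome measure of the trial.

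**Working it through.** The plan gives no figure for this point, so there is none to reproduce. The check is to list the sign patterns and match them to the rows of Appendix 2.

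**Inputs.** Five signs, each present or absent: pain, redness, swelling, palpable cord, pyrexia (Appendix 2; the same five are in Section 4.3). This gives 2^5 = 32 patterns.

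**Exact reading** (a row applies only if its signs and no others are present, ignoring the words for slight and extensive):

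- no sign, 1 pattern (score 0)
- pain only or redness only, 2 (score 1)
- exactly two of pain, redness and swelling, 3 (score 2)
- all three, 1 (score 3)
- all three plus cord, 1 (score 4)
- all five, 1 (score 5)

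Total 1 + 2 + 3 + 1 + 1 + 1 = 9 of 32.

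**Lenient reading** (a cord or pyrexia is ignored unless pain, redness and swelling are all present, so the rest of the pattern sets the score). There are 4 states of cord and pyrexia.

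- at least two of pain, redness and swelling: 4 × 4 = 16, scored
- pain only or redness only among the three: 2 × 4 = 8, scored
- no sign at all: 1, scored
- swelling only among the three: 1 × 4 = 4, **not scored**
- none of the three, but cord and/or pyrexia: 3, **not scored**

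Scored 16 + 8 + 1 = 25; unscored 4 + 3 = 7; 25 + 7 = 32.

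**Local signs only.** Leaving pyrexia out gives 2^4 = 16 patterns. On the lenient reading 3 have no score: swelling alone, cord alone, and swelling plus cord.

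**Does row 0 absorb them?** No. It requires a healthy-looking site with no signs of phlebitis, and Section 1 names oedema and cords as such signs.

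**Can the score be rebuilt later?** Not from the form. Besides the VIP score, each time point has fields for treatment applied, infusions and other drugs, and initials. The removal block has one free reason field. None holds individual signs. The undertaking in Section 8.2(b) therefore has no matching field.

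**Worst-case illustration.** All inputs are assumptions: no true effect, 20% incidence, incidence meaning a score of 1 or more, and a fraction u of patients whose only finding is unscorable and is scored 0 in every sesame patient and 1 in every control. The apparent risk ratio is (0.20 − u) / 0.20. Type I error is that of a two-sided uncorrected chi-square test at 5%.

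| u | Risk ratio | Type I error, N = 650 | Type I error, N = 100 |
|---|---|---|---|
| 1% | 0.19 / 0.20 = 0.95 | 6% | 5% |
| 3% | 0.17 / 0.20 = 0.85 | 17% | 7% |

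If these patients are instead scored 0 in both arms, the true null is preserved (risk ratio 1) and type I error stays at about 5%. The inflation comes from the assumed opposite scoring by arm.

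**The case against.** Several parts of the case against have force.

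- **No cut-off is stated.** The documents do not say which VIP score counts as incident phlebitis. Appendix 2 calls score 1 only a possible first sign. If incidence meant 2 or more, choosing between 0 and 1 for an isolated sign would not change it. This stands. Swelling plus cord could still be placed on either side of a cut at 2, and severity is affected under any cut-off.
- **A screen may be stricter than an outcome.** Section 4.3 does not say that each sign alone is phlebitis, and swelling may have other causes, such as infiltration. This is fair, but Section 1 supplies the link for oedema and cords. If the team means isolated swelling not to count, the tool still has to say so.
- **Pyrexia differs.** Section 1 mentions it only within the most severe grade, and fever in an inpatient need not come from the cannula site. This stands, and isolated pyrexia should not become a phlebitis event.
- **Symptoms are to be documented.** Section 8.2(b) does promise this, so the plan does not ignore the matter. What is missing is a place on the form to do it.

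A reader might also infer that these sites will be recorded as 0. The documents do not say so, and row 0 does not fit; a score of 0 is one possible choice. A reader might add that a single marked sign, such as strong redness alone, is also unscored. That depends on reading the word slight as excluding anything stronger. An assessor could reasonably use score 1, and the counts of 7 of 32 and 3 of 16 do not rely on it.

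**Conclusion.** The gap is real and can be read directly from Appendix 2. Swelling alone, a palpable cord alone, and the two together without pain or redness have no score. These are 3 of 16 local-sign patterns (7 of 32 with pyrexia), even on the lenient reading. The score is left to the investigators who also apply the oil, and the form does not allow it to be re-derived.

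The counts are of patterns, not of patients. The documents give no frequency for these findings, so the amount of misclassification cannot be computed, and its effect on incidence depends on the unstated cut-off. A reader might take the risk ratio of 0.85 or the 17% type I error as the size of the problem. The documents do not support that. Both figures need an assumed frequency, a cut-off of 1 and opposite scoring by arm, and the gap handled alike in both arms does not produce them. The point should be corrected because it concerns the sole outcome measure and cannot be repaired once visits have been recorded as totals only.

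**What to change.** In the data collection form (Appendix 3), record pain, redness, swelling, palpable cord and pyrexia separately at each time point. Allow a not-assessable entry for the cord at phone or video follow-up, which Section 5 permits after discharge.

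In Appendix 2 or Section 8.2, add one fixed rule that derives the VIP score from these entries. It should be set before data are analysed and applied identically in both arms. It should:

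- give every pattern of local signs a score, with isolated swelling or an isolated cord at least 1;
- say how a single pain or redness sign that is more than slight is scored;
- say how a cord that could not be assessed is handled;
- keep pyrexia as a recorded item, without letting isolated pyrexia count as phlebitis by default.

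State the VIP score from which a site counts as incident phlebitis.

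The cost is a longer form: the form has nine time points, so 5 × 9 = 45 short entries in place of 9 scores. Scores also become slightly less comparable with the unmodified tool, from which the study has already departed. The change concerns outcome scoring only; the action column of the tool is not addressed here.
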